1.6 Obesity and prostate cancer

Two-thirds of the adult male population in the US is overweight or obese⁶⁴ and excess bodyweight deregulates several pathways such as insulin levels, free insulin growth factor 1 (IGF-1), adiponectin, and sex hormones that could potentially affect prostate cancer outcomes. Several studies have demonstrated association between obesity and the incidence of prostate and other cancers⁶⁵. It has been postulated that increased insulin resistance and adipokines may play an important role⁶⁶. Circulating levels of adiponectin and leptin in obese patients may also be important in prostate cancer pathogenesis⁶⁷. Adiponectin levels (inhibitory adipokine) are reduced in obese patients, while leptin levels are increased, which at the end may promote prostate cancer growth⁶⁸. This theory is supported by evidence showing that hyperinsulinemia upregulates insulin receptors in PCa cells and increases tumor growth⁶⁹. Hyperinsulinemia and metabolic syndrome may play a role in carcinogenesis and be negatively associated with prostate cancer prognosis⁷⁰. Increased insulin level decreases sex hormone-binding globulins, and causing an increase in free unbound androgens which at the end may lead to worse prognosis⁷¹. In prostate cancer patients treated with RP, obesity was associated with higher-grade tumors, a trend toward increased risk of positive surgical margins, and higher biochemical failure rates⁷². In diabetic patients, obesity is associated with higher risk of high-risk prostate cancer, which is independent of the lower risk for prostate cancer in diabetic patients⁷³. The lower risk for prostate cancer in diabetic patients is possibly explained by lower levels of testosterone in these patients⁷⁴. Another retrospective study showed that the presence of metabolic syndrome was associated with a shorter median time to progression (16 vs 36 months) and median OS (36.5 vs. 46.7 months) in prostate cancer patients receiving ADT⁷⁵.

Cao and Ma recently reported a meta-analysis of six post-diagnosis survival studies on 18,203 patients with 932 deaths and found that 5 kg/m² increase in BMI was associated with 20% higher prostate cancer-specific mortality. The sixteen studies followed 26,479 prostate cancer patients after their primary treatment, a 5 kg/m² increase in BMI was significantly associated with 21% increased risk of BCR (RR: 1.21, 95% CI: 1.11-1.31 P < 0.01). This study demonstrated that elevated BMI is associated with increased risk of biochemical recurrence and prostate cancer-specific mortality⁷⁶. Unanswered question is does weight loss reduce the risk of recurrence, the development of metastases, and death from prostate in men with the disease?

1.7 Rationale and Hypothesis

Obesity and metabolic syndrome are prevalent among prostate cancer patients. Hyperinsulinemia is associated with a shorter median time to progression and median OS in patient with biochemical recurrence. Early ADT is frequently used in this patient population, with no proven benefit, which may increase mortality and morbidity.

Metformin is an inexpensive and safe drug that may have anticancer activity through

both insulin-dependent and insulin-independent mechanisms, which involve activation of adenosine monophosphate (AMP)-activated protein kinase (AMPK), inhibiting mTOR signaling pathway⁷⁷. Recent evidence suggests activation of AMPK leads to down regulation of AR⁷⁸ and inhibits xenograft growth of several PCa cell lines⁵⁴. Metformin should work better in early, castrate sensitive prostate cancer since in castration resistant disease AR signaling is increased (through amplification, mutations, and intracellular androgen stimulation) which may hamper metformin's ability to inhibit cancer growth.

Bicalutamide is a non-steroidal antiandrogen, which functions by blocking the AR. It exerts its effect predominantly through induction of a G1/S phase arrest of the cell cycle⁷⁹. Published preclinical data suggest the additive anticancer effects of combining metformin and bicalutamide in the prostate cancer patients with metabolic syndrome and possible synergistic activity with antiandrogens: in AR-positive cells, this effect appeared to be mediated by reducing proliferation rates by modulating the AR, whereas in AR-negative cells the combination treatment appeared to promote apoptosis.

HYPOTHESIS:

Metformin will enhance the antitumor effects of the antiandrogen bicalutamide in the setting of preserved testosterone, effectively delaying onset of metastases while preserving quality of life in overweight and obese men with castrate naïve non-metastatic prostate cancer with biochemical recurrence.

2.0 OBJECTIVES

2.1 Primary endpoint:

The proportion of patients with undetectable PSA (< 0.2 ng/mL) at 32 weeks with metformin plus bicalutamide compared to bicalutamide monotherapy.

2.2 Secondary endpoints:

- The proportion of patients with PSA decline > 85% at 32 weeks with metformin plus bicalutamide compared to bicalutamide monotherapy.
- The time to PSA progression with metformin plus bicalutamide compared to bicalutamide monotherapy.
- To evaluate the time to onset of radiographic evidence of metastatic disease (rPFS) with metformin plus bicalutamide compared to bicalutamide monotherapy.
- To characterize the PSADT changes pre-study, during treatment, and off treatment.
- To evaluate the safety and tolerability of metformin in this patient population.
- To evaluate QOL with metformin plus bicalutamide compared to bicalutamide monotherapy.
- To evaluate the time to next therapy (i.e. antiandrogen or GnRH antagonist/agonist).

2.3 Exploratory endpoints:

- Immunogenicity of bicalutamide +/- metformin by flow cytometric analysis of T-cell frequency, activation status, cytokine profiles, antibody levels and analysis of sCD27 and sCD40L
- Evaluate circulating PSA levels and correlations with immunogenicity and/ or efficacy

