3.0 PATIENTS SELECTION

3.1 Inclusion Criteria

- 3.1.1** Ability to understand and the willingness to sign a written informed consent.
- 3.1.2** Male 18 years or older.
- 3.1.3** Histologically or cytologically confirmed diagnosis of prostate cancer.
- 3.1.4** Patient must have had previous treatment with definitive surgery or radiation therapy or cryoablation.
- 3.1.5** Patient may have prior salvage therapy (surgery, radiation or other local ablative procedures) within 6 months prior to randomization if the intent was for cure. Prophylactic radiotherapy to prevent gynecomastia within 4 weeks prior to randomization is allowed.
- 3.1.6** Patient may have had prior neoadjuvant and/or adjuvant therapy (chemotherapy, vaccines or experimental agents) within 4 weeks prior to randomization, if the PSA rise and PSADT were documented after the testosterone level was > 150 ng/dL.
- 3.1.7** Patients may have had therapy modulating testosterone levels (such as luteinizing-hormone, releasing-hormone agonists/antagonists and antiandrogens) in the past as long as the testosterone level is > 150 ng/dL within 4 weeks of trial entry. Agents such as 5 alpha reductase inhibitors, ketoconazole, abiraterone, systemic steroids, or herbal supplements known to decrease PSA levels including any dose of Megestrol acetate, Finasteride (e.g., Saw Palmetto and PC-SPES, African pygeum extract, lycopene, alanine, glutamic acid and glycine, beta-sitosterol, lycopene, nettle root extract, quercitin, Belizian Man Vine extract, mulra puama extract and epimedium extract Campesterol, Beta- sitosterol, Stigmasterol, Sitostanol and Brassicasterol) are not permitted at any time during the period that the PSA values are being collected.
- 3.1.8** Patient must have hormone-sensitive prostate cancer as evident by a serum total testosterone level > 150 ng/dL within 12 weeks prior to randomization.
- 3.1.9** PSA must be < 30 ng/mL at study entry.
- 3.1.10** Patient must have evidence of biochemical failure after primary therapy and

subsequent progression. Biochemical failure is declared when the PSA reaches a threshold value after primary treatment and it differs for radical prostatectomy or radiation therapy.

- For radical prostatectomy the threshold for this study is $PSA \geq 0.2$ ng/mL
- For radiation therapy the threshold is a PSA rise of 2 ng/mL above the nadir PSA achieved post radiation with or without hormone therapy (2006 RTGO-ASTRO Consensus definition).

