7.0 MEASUREMENT OF EFFECT

7.1 Definitions of Biochemical Response and Progression

7.1.1 Complete Response: PSA <0.2 ng/mL confirmed on two consecutive

26

additional determinations taken at least 4 weeks apart.

7.1.2 *Partial Response:* A reduction in PSA $\geq 50\%$ from baseline without evidence of clinical or radiographic progression confirmed on two consecutive additional determinations taken at least 4 weeks apart.

7.1.3 *Stable Disease:* Patients who do not meet the criteria for response (CR or PR) or serological progression for at least 3 months (90 days) will be categorized as having stable disease.

7.1.4 *Progressive Disease:*

1) For patient who achieved a $\geq 50\%$ decline in PSA, progression is defined as an increase in PSA value by 50% above baseline or nadir (whichever is lowest), confirmed by a second PSA rise at least two weeks later. The PSA rise must be at least 5 ng/mL. Changes in PSA below 5 ng/mL will not be considered assessable for progression.

2) For patients with an undetectable PSA nadir (< 0.2 ng/mL), progression is defined as a PSA rise to the detectable range (detectable PSA is ≥ 0.2 ng/mL) confirmed by a second PSA rise at least 2 weeks later.

3) For patients whose PSA has not decreased by 50%, progression is defined as an increase in PSA value $\geq 50\%$ of baseline (on trial) or nadir PSA, whichever is lowest, confirmed by a repeat PSA at least 2 weeks later. The PSA must have risen by at least 5 ng/mL.

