11.3 Secondary assessments

We will test the hypothesis that the fraction of arm A and arm B patients with at least 85% reduction in PSA at 32 weeks will be the same. We will sort the 66 patients 32 week PSAs into groups above or below their grand median 32 week PSA. We will then submit the doubly dichotomized data to Fisher's exact test. The test will distinguish an odds ratio of 3.19 from one of 1.0 with 80% power and at most 10% type I error.

We will characterize the time to PSA progression and the time to onset of metastatic disease using the method of Kaplan and Meier. We will compare arms A and B for each of these end points with log-rank tests. Patients will be followed for PSA progression and for onset of metastatic disease for at least 60 months.

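### The >85% PSA decline endpoint has no rule for results below the reporting limit; if that limit is 0.2 ng/mL, the decline cannot be verified for men entering below 1.33 ng/mL

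*Combined protocol and SAP*

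**What the plan says.** The primary endpoint in section 2.1 is "The proportion of patients with undetectable PSA (< 0.2 ng/mL) at 32 weeks". The first secondary endpoint in section 2.2 is "The proportion of patients with PSA decline > 85% at 32 weeks". Section 11.3 words the criterion slightly differently, as "patients with at least 85% reduction in PSA at 32 weeks".

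Section 7.1.4 says "detectable PSA is ≥ 0.2 ng/mL", and for men with an undetectable nadir "progression is defined as a PSA rise to the detectable range". Section 7.1.1 defines complete response by the same 0.2 cut-off, with confirmation, and asks for no percentage fall.

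On entry, section 3.1.9 gives only an upper bound: "PSA must be < 30 ng/mL at study entry". Section 3.1.10 sets the failure threshold by prior treatment. "For radical prostatectomy the threshold for this study is" 0.2 ng/mL or more; after radiation it is 2 ng/mL above the nadir. Section 3.1.11 adds two consecutive rises above the threshold and a doubling time of 3 to 12 months. Section 3.1.4 also admits men treated with cryoablation, for whom 3.1.10 gives no threshold.

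The documents do not give the assay's reporting limit, a way to turn a result below that limit into a percentage decline, or the baseline value for the decline. The same-laboratory rule in 3.1.11 covers baseline PSAs only.

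**The concern.** A post-prostatectomy man can enter with a PSA only a little above 0.2 ng/mL. An 85% fall from such a value lies below the level that the protocol calls detectable. If the laboratory reports only that his week-32 PSA is below 0.2, his percentage decline is unknown, and nothing in the plan says how to score him. One analyst could call him a responder, another a failure, and a third could treat him as missing.

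This choice would fall on men with a good PSA outcome, in one part of the population. Scoring them as failures would hide true responders in both arms and weaken the comparison. The result could also depend on which laboratory a site uses.

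**Working it through.** **Plan's own figure.** Section 11.3 claims 80% power for an odds ratio of 3.19 at a type I error of at most 10%, with 66 men (nominally 22 and 44). It does not state sidedness. For a median split the pooled rate is 50%, which with that odds ratio gives 31.4% vs 59.3%. The one-sided 10% normal approximation then gives 81.8%, close to the stated 80%. The two-sided version gives 70.0%. The stated power is therefore not in dispute if the test is one-sided.

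**Entry cut-off.** Let L be the lowest value the laboratory reports. A result below L proves a fall of more than 1 − L/entry. This reaches 85% only when entry is at least L/(1 − 0.85) = L/0.15. The documents do not give L, so a range is assumed:

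| Assumed L (ng/mL) | Cut-off L/0.15 (ng/mL) |
|---|---|
| 0.2 | 1.33 |
| 0.1 | 0.67 |
| 0.05 | 0.33 |
| 0.02 | 0.13, below the 0.2 prostatectomy threshold, so nobody is affected |

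**What a result below 0.2 proves when L = 0.2:**

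| Entry PSA | Week-32 PSA needed (15% of entry) | Fall proved: more than |
|---|---|---|
| 0.3 | 0.045 | 33% |
| 0.5 | 0.075 | 60% |
| 1.0 | 0.15 | 80% |
| 1.34 | 0.201 | 85.1% |
| 2.0 | 0.30 | 90% |

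**Who is affected.** Post-radiation men must reach nadir + 2, so at least 2 ng/mL, which is above 1.33. Post-prostatectomy men can enter anywhere from just above 0.2. Cryoablation cannot be placed without a threshold.

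**Share of men (assumption only).** The documents give neither an entry-PSA distribution nor a split by prior therapy. Suppose 40–80% are post-prostatectomy, with lognormal entry PSA (median 0.6–2.0, log SD 1, truncated to 0.2–30). Then about 13–60% of all men enter below 1.33 and 5–38% below 0.67. The width of these ranges shows that the share is not known.

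**Power (hypothetical).** Take a one-sided 10% Fisher test of the 85% criterion itself, 22 vs 44 men, with assumed true rates of 40% vs 68%. Their odds ratio is (0.68/0.32)/(0.40/0.60) = 3.19. Suppose a share f of responders in both arms is scored as failures:

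- f = 0: 40% vs 68%, exact power 75.6%
- f = 20%: 0.40 × 0.8 = 32% vs 0.68 × 0.8 = 54.4%, power 60.3%
- f = 40%: 0.40 × 0.6 = 24% vs 0.68 × 0.6 = 40.8%, power 43.0%

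The share f is chosen for illustration and does not follow from the shares of entrants above.

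**The case against.** The strongest reply is that 0.2 is a clinical cut-off. Nowhere do the documents call it a limit of quantification, and with a fine enough assay the problem shrinks or disappears. That stands, and the conclusion must stay conditional on the reporting limit. What remains is that the plan neither states the limit nor says what to do with a result below it.

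A reader might infer that every man who meets the primary endpoint but misses the 85% criterion is misclassified. The documents do not support this. A measured fall from 1.0 to 0.19 is 81%, and from 0.3 to 0.19 it is 37%. Both are rightly not declines above 85%, because the two endpoints measure different things. Only censored results hide a true responder.

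A reader might also infer that the test in 11.3 would count undetectable men as failures. It would not. It splits raw week-32 PSA at the grand median. At the design rates in 11.1, 20% of 22 plus 40% of 44 is 4.4 + 17.6 = 22 of 66 men undetectable. That is one third, so all of them fall on the favourable side. The written test does not score the 85% endpoint at all. This is a separate mismatch that needs its own correction, and a test corrected to score the 85% criterion would meet the problem described here.

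The consequence is also limited. Section 1.2 prefers undetectable PSA and offers the 85% decline as an additional, exploratory measure. The primary endpoint is untouched. Section 11.1 stratifies by prior therapy, so affected men should be roughly balanced, and the expected harm is lost sensitivity with no systematic bias between arms.

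**Conclusion.** The point holds conditionally. If no value below 0.2 ng/mL is reported, a decline above 85% cannot be verified for a man entering below 1.33 ng/mL, and the plan has no rule for scoring him. The cut-off falls in proportion to the reporting limit. The gap is confined to post-prostatectomy men and possibly those treated with cryoablation.

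The number of men affected cannot be obtained from the documents. The fall in power from 76% to between 60% and 43% shows what would follow if 20–40% of responders in both arms were lost at the assumed rates; it does not estimate what will happen in this trial. The calculations use entry PSA as the baseline, which the plan should confirm. This is an inexpensive clarification of one secondary endpoint.

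**What to change.** In sections 2.2 and 11.3:

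1. Record the numeric week-32 PSA and the laboratory's reporting limit for each man.
2. Score the decline from the numeric value wherever one is reported.
3. Where the result is below the reporting limit and 15% of entry PSA also lies below that limit, count the man as meeting the decline.
4. Alongside this, report the same comparison restricted to men with entry PSA of at least 1.34 ng/mL, where a result below 0.2 always proves the fall.

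Correct the grand-median test separately, so that 11.3 tests the endpoint named in 2.2, and use one form of the criterion (above 85%, or at least 85%) in both places.

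The cost is some wording, one extra data field and one extra table, with no added patients or visits. The downside is that some men with low entry PSA may qualify with a smaller true fall. The restricted comparison shows whether that matters, but it uses fewer than the 66 men and is less precise. Counting every undetectable man as a decliner would go too far: a measured change from 0.21 to 0.19, a fall of about 10%, would then qualify. For that reason step 3 applies only to censored results.

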3.0 PATIENTS SELECTION

3.1 Inclusion Criteria

- 3.1.1** Ability to understand and the willingness to sign a written informed consent.
- 3.1.2** Male 18 years or older.
- 3.1.3** Histologically or cytologically confirmed diagnosis of prostate cancer.
- 3.1.4** Patient must have had previous treatment with definitive surgery or radiation therapy or cryoablation.
- 3.1.5** Patient may have prior salvage therapy (surgery, radiation or other local ablative procedures) within 6 months prior to randomization if the intent was for cure. Prophylactic radiotherapy to prevent gynecomastia within 4 weeks prior to randomization is allowed.
- 3.1.6** Patient may have had prior neoadjuvant and/or adjuvant therapy (chemotherapy, vaccines or experimental agents) within 4 weeks prior to randomization, if the PSA rise and PSADT were documented after the testosterone level was > 150 ng/dL.
- 3.1.7** Patients may have had therapy modulating testosterone levels (such as luteinizing-hormone, releasing-hormone agonists/antagonists and antiandrogens) in the past as long as the testosterone level is > 150 ng/dL within 4 weeks of trial entry. Agents such as 5 alpha reductase inhibitors, ketoconazole, abiraterone, systemic steroids, or herbal supplements known to decrease PSA levels including any dose of Megestrol acetate, Finasteride (e.g., Saw Palmetto and PC-SPES, African pygeum extract, lycopene, alanine, glutamic acid and glycine, beta-sitosterol, lycopene, nettle root extract, quercitin, Belizian Man Vine extract, mulra puama extract and epimedium extract Campesterol, Beta- sitosterol, Stigmasterol, Sitostanol and Brassicasterol) are not permitted at any time during the period that the PSA values are being collected.
- 3.1.8** Patient must have hormone-sensitive prostate cancer as evident by a serum total testosterone level > 150 ng/dL within 12 weeks prior to randomization.
- 3.1.9** PSA must be < 30 ng/mL at study entry.
- 3.1.10** Patient must have evidence of biochemical failure after primary therapy and

subsequent progression. Biochemical failure is declared when the PSA reaches a threshold value after primary treatment and it differs for radical prostatectomy or radiation therapy.

- For radical prostatectomy the threshold for this study is $PSA \geq 0.2$ ng/mL
- For radiation therapy the threshold is a PSA rise of 2 ng/mL above the nadir PSA achieved post radiation with or without hormone therapy (2006 RTGO-ASTRO Consensus definition).
- PSA progression requires a PSA rise above the threshold measured at any time point since the threshold was reached.

3.1.11 PSA doubling time between 3 and 12 months. PSA calculation requires at least two consecutive PSA rises (PSA2 and PSA3) above the threshold PSA (at least 3 PSA values); PSA2 and PSA3 must be obtained within 12 months of study entry. All baseline PSAs should be obtained at the same reference lab. Patient's PSA doubling time must be calculated using the following formula (<http://www.mskcc.org/nomograms/prostate/psa-doubling-time>):

$$\text{PSADT in days} = \frac{0.693 (t)}{\ln (PSA3) - \ln (PSA2)}$$

Where t = the number of days between PSA3 and PSA2

ln = the natural log

PSADT in months = PSADT in days divided by 30.4375

3.1.12 ECOG performance status 0 to 2.

3.1.13 Ability to swallow the study drugs.

3.1.14 Subjects must have normal organ and marrow function as defined below:

- Absolute neutrophil count $\geq 1,000$ /mL
- Hemoglobin ≥ 10 g/dL
- Platelets $\geq 100,000$ /mL
- Total bilirubin within normal institutional limits
- AST(SGOT)/ALT(SGPT) ≤ 1.5 X institutional ULN
- Creatinine clearance ≥ 60 mL/min/1.73 m²
- Hgb A1c $\leq 6.5\%$

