3.2 Exclusion Criteria

3.2.1 Evidence of metastatic disease on imaging studies (CT, x-ray, and/or bone scan).

3.2.2 Diagnosis of diabetes mellitus defined as:

- Fasting blood glucose > 126 mg/dl or,
- Random blood glucose > 200 mg/dl
- Hemoglobin A1C $> 6.5\%$

- 3.2.3** Need for treatment with any conventional modality for prostate cancer (surgery, radiation therapy, and hormonal therapy).
- 3.2.4** Treatment with any investigational drug 30 days prior to randomization.
- 3.2.5** Radiation therapy within prior 6 months (prophylactic radiotherapy to prevent gynecomastia within 4 weeks prior to randomization is allowed).
- 3.2.6** Known hypersensitivity to metformin.
- 3.2.7** Prior history of lactic acidosis.
- 3.2.8** Any history of myocardial infarction in the past 12 months.
- 3.2.9** Subjects who consume more than 3 alcoholic beverages per day.
- 3.2.10** Subjects with serious intercurrent illness, including, but not limited to, ongoing or active infection, symptomatic congestive heart failure, unstable angina pectoris, cardiac arrhythmia, or other nonmalignant medical or psychiatric illness that is uncontrolled or whose control may be jeopardized by the complications of this therapy or may limit compliance with the study requirements (at the discretion of the investigator).
- 3.2.11** Patient with previous or concurrent malignancy. Exceptions are made for patients who meet any of the following conditions: Basal cell or squamous cell carcinoma of the skin or prior malignancy that has been adequately treated and patient has been continuously disease free for ≥ 2 years.
- 3.2.12** Subjects currently treated with metformin and/or bicalutamide or who have been treated with metformin and/or bicalutamide in the past 6 months.
- 3.2.13** Subjects who have taken 5 α -reductase inhibitors (finasteride or dutasteride), saw palmetto, or PC-SPES within the last 6 weeks are ineligible. Subjects will be eligible for the study after the wash out period of 6 weeks.

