11.0 STATISTICAL CONSIDERATIONS

11.1 Sample size

We will test the hypothesis that only 20% of patients on either arm of the study will have undetectable PSA at 32 weeks, versus the alternative that 40% of arm B patients will. An initial cohort of 39 patients and, if continued, a second cohort of 27 patients will be randomized 2:1 to arms B and A respectively.

After stratification for prior therapy we will randomize, 2:1, nominally 13 patients to arm A and 26 patients to arm B. Because of post stratification randomization, the exact numbers in the two arms may vary slightly from 13 and 26, but the total patient number in the the initial cohort will be exactly 39 and the final sample number be exactly 66. Our intent is to compare the proportions of patients with undetectable PSA at 32 weeks. This is most simply described by the difference $(E1/26) - (C1/13)$, where C1 and E1 are the numbers of undetectable PSAs in arms A and B respectively. The cut point for continuation of the trial past the first cohort requires that

$(E1/26) - (C1/13) > -2/13 = -0.1538462\dots$. To avoid confusion due to round off of such fractions, we identify the decision boundary by $13 E1 - 26 C1 > -52$, exactly equivalent the first expression, and obtained by multiplying all terms by $13*26$.

If $13 E1 - 26 C1$ exceeds -52 AND $E1$ is at least 6 then we will randomize an additional 9 patients to arm A and 18 patients to arm B. Otherwise the study will be terminated and the null hypothesis accepted. Letting $C2$ and $E2$ be the numbers of undetectable PSAs in the second cohort, we will finally reject the null hypothesis if $22(E1 + E2) - 44(C1 + C2)$ is at least 88 and $E1 + E2$ is at least 14. The initial cohort will consist of 39 and the final cohort of 27 patients for a total of 66 patients. If the true null is 20% undetectable PSAs type I error will be 3.24% and power will be 80.3%. In this case the chance of early stopping under the null will be 60% but will be 3.23% if the true arm B fraction of undetectable PSAs is 40%.

If the null (arm A) fraction undetectable PSAs is 25% type I error increases to 10.9% and power increases to 83.3% if the arm B fraction undetectable is 45% (20% higher). If the null fraction is 30% type I error increases to 19.7% and power to 83.2% (arm B 50%, 20% higher).

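### Inclusion 3.1.5 and exclusion 3.2.5 conflict on recent salvage radiation, and no criterion requires the qualifying PSA rises to follow recent salvage treatment

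*Combined protocol and SAP*

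**What the plan says.** Section 3.1.5 reads "Patient may have prior salvage therapy (surgery, radiation or other local ablative procedures) within 6 months prior to randomization", on condition that the intent was curative. It names no minimum interval since the salvage treatment. Section 3.2.5 excludes "Radiation therapy within prior 6 months (prophylactic radiotherapy to prevent gynecomastia within 4 weeks prior to randomization is allowed"). Both criteria carry the same gynecomastia exception, and neither says which prevails.

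The PSA entry criteria are these:

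- 3.1.9 caps PSA at study entry below 30 ng/mL and sets no lower limit.
- 3.1.10: "Biochemical failure is declared when the PSA reaches a threshold value after primary treatment". It adds "PSA progression requires a PSA rise above the threshold measured at any time point since the threshold was reached".
- 3.1.11 asks for two consecutive rises and a doubling time of 3 to 12 months. On timing it says only "PSA2 and PSA3 must be obtained within 12 months of study entry".

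The primary endpoint (2.1) is PSA below 0.2 ng/mL at 32 weeks. Section 11.1 tests a common rate of 20% against 40% in arm B, with a fixed two-stage rule on 39 and then 66 men, randomised 2:1 after stratification for prior therapy. It gives type I error of 3.24% at the 20% null and warns that if the null "fraction undetectable PSAs is 25% type I error increases to 10.9" percent, with 19.7% at a 30% null.

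**The concern.** Two sites can read the criteria differently and enrol different men. The larger statistical issue is what recent curative-intent local treatment does to the endpoint. It can itself bring PSA below 0.2 ng/mL by week 32, whatever the arm. A man whose PSA is already falling for that reason says little about metformin, and he raises the background rate of success.

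The decision rule does not adapt to that rate. Its boundaries were set for 20%, and false-positive risk climbs quickly above it, as the plan itself reports. Entry of such men therefore bears on the type I error even when they are evenly spread over the arms.

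**Working it through.** **1. Which treatments are admitted.**

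| Salvage treatment in the 6 months before randomisation | 3.1.5 | 3.2.5 | Result |
|---|---|---|---|
| Radiation | allowed | excluded | contradictory; out if every exclusion is applied |
| Surgery | allowed | silent | admitted |
| Other local ablation | allowed | silent | admitted |

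**2. Whether the PSA criteria stop such a man.** Take illustrative values (an assumption): PSA2 = 0.5 ng/mL at month −12 and PSA3 = 0.8 ng/mL 120 days later, about month −8. By the formula in 3.1.11,

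PSADT = 0.693 × 120 / ln(0.8/0.5) = 177 days; 177 / 30.4375 = 5.8 months.

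This is inside 3 to 12 months. Only the ratio of the two values enters, so higher PSA levels in the same ratio give the same answer. Salvage surgery or ablation at month −5 then satisfies 3.1.5. Failure under 3.1.10 was met after primary therapy, both rises fall in the 12-month look-back, and no lower PSA limit applies at entry. None of these criteria requires a rise after the salvage treatment. By contrast, 3.1.6 does anchor the PSA rise and doubling time to an earlier event, recovery of testosterone above 150 ng/dL.

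**3. Reproducing the plan's operating characteristics.** Enumerate C1, E1, C2 and E2 as independent binomials (13 and 26 men, then 9 and 18 more). Continue if 13·E1 − 26·C1 > −52 and E1 ≥ 6. Reject if 22(E1+E2) − 44(C1+C2) ≥ 88 and E1+E2 ≥ 14.

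| Null rate | Type I error, recomputed | Plan | Power (+20 points), recomputed | Plan |
|---|---|---|---|---|
| 20% | 3.25% | 3.24% | 80.4% | 80.3% |
| 25% | 10.98% | 10.9% | 83.4% | 83.3% |
| 30% | 19.70% | 19.7% | 83.3% | 83.2% |

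The plan's figures are reproduced to within 0.1 point.

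**4. Effect of k affected men among 66.** The documents give neither k nor the undetectable rate of such men. Assume 60% of them are undetectable in either arm, that the others follow the 20% null, and that affected men are spread at random over the arms. The common null rate is

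p = 0.20 + (0.60 − 0.20) × k/66.

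| k | p | Type I error |
|---|---|---|
| 0 | 20.0% | 3.25% |
| 1 | 20.6% | 3.9% |
| 2 | 21.2% | 4.7% |
| 3 | 21.8% | 5.6% |
| 8 | 24.8% | 10.7% |

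If only 40% of such men are undetectable, three of them give p = 0.20 + 0.20 × 3/66 = 20.9% and type I error of 4.3%.

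**The case against.** Four points on the other side carry weight.

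- **Radiation.** 3.1.5 is permissive and 3.2.5 is an exclusion. On the usual reading every exclusion applies, and no man with salvage radiation in the window enters. The shared gynecomastia exception suggests one intended rule worded two ways. A reader might infer that the plan means to enrol recently irradiated men; the documents do not support that. What stands is that the text contradicts itself and leaves the choice to the site.
- **The remaining route is narrow.** Section 1.1 describes salvage prostatectomy as an option in selected cases after radiation. The man must also have documented failure, two consecutive rises and a qualifying doubling time, and under 3.2.3 no need for conventional treatment. These limits are real, and nothing in the documents suggests that such entries are common. They still do not require a rise after salvage.
- **Balance.** A reader might infer a bias towards arm B. Randomisation is stratified for prior therapy, so such men should be balanced on average and no directional bias follows. Balance does not restore the type I error, because the boundary assumes a 20% common rate.
- **Size.** A reader might carry the plan's 10.9% over as the effect of this flaw. Under the assumptions above, that needs about eight affected men. With one or two, type I error stays below 5%. The sensitivity to the null rate is general, and section 11.1 discloses it openly.

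**Conclusion.** The contradiction between 3.1.5 and 3.2.5 is certain. So is the gap that leaves recent salvage surgery and ablation admissible with PSA rises that pre-date them. The consequence for the primary test is conditional. Section 11.1 says type I error is below 5% for every possible split between the arms at its design null. At 60% undetectable, three affected men are enough to pass that level (5.6%); at 40%, three are not (4.3%). These figures rest on assumed numbers of men and assumed rates, so the documents support neither a claim that the test is materially inflated nor a claim that it is safe. The point merits correction because the endpoint is directly exposed and the remedy is small.

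**What to change.** 1. Reconcile 3.1.5 and 3.2.5 so that one rule covers all salvage local therapy: radiation, surgery and ablation. The interval is the sponsor's decision.
2. Require the PSA rises and doubling time that qualify a man under 3.1.10 and 3.1.11 to be documented after his most recent local therapy, in the way 3.1.6 already does for testosterone recovery.
3. List any man already enrolled with salvage therapy inside the window, and report a supportive sensitivity analysis without such men. Give the difference in proportions with an exact confidence interval. The boundaries tabulated in section 11.1 cannot be reused, since they hold only for totals of 39 and 66.

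The cost is a change of eligibility wording, one additional analysis and possibly a small loss of accrual.
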